Data analysis and sample Size Justification. Drs. [name] and [name] will guide me in the analysis of Aim 2. We will use R software to upload and analyze quantitative data. 99 All electronic data will be stripped of identifiers and stored in password-protected files at the KU ADC and will be accessible only to research staff. Alianza Latina's primary outcomes will be assessed using simple descriptive statistics. The primary quantitative feasibility/process endpoints are dichotomous measures, so the proportions will be estimated as the main statistical results. Results will include 95% confidence intervals based on an exact binomial distribution. With an anticipated 50/100 PCPs integrating Alianza Latina screenings to their regular workflow and 100/135 newly referred Latino ADRD dyads who enroll in Health Navigator services, our confidence intervals will be within approximately ±11.0% and ±7.4%, respectively, of their estimated proportions. These proportions have been chosen based on clinically significant levels estimated in consensus between my mentors and I and from the literature. 30 Because this is a feasibility study, the sample size was not fully-powered to test a hypothesis but allow a sufficiently accurate estimation of these important processes measures to inform the subsequent R01 application. At the end of the study, my mentors, consultants and I will meet and review all results to make modifications to the intervention and study design and calculate the appropriate sample.

Table 3. Feasibility and acceptability outcomes in Aim 2

Outcome	Data source	Operationalization
PCP training	Metrics (recruitment)	Number of PCPs who agree to be trained per month
Feasibility	Metrics (retention)	% of PCPs followed up
	PCP FU survey & metrics (fidelity)	% able to implement screenings in regular workflow;
		Number of referrals to Health Navigator per month
	Metrics (assessment process)	% of PCPs who complete BL and FU surveys about ADRD
		knowledge, attitudes and skills
	Metrics (treatment adherence)	% of PCPs who complete training
Acceptability	PCP FU survey	5-item Likert scales on satisfaction with training
ADRD care	Metrics (recruitment)	% of referred Latino ADRD dyads who enroll in Health Navigator
Feasibility	, ,	services
	Metrics (retention)	% of referred Latino ADRD dyads followed up at 6m
	Metrics (assessment process)	% of planned BL and FU survey ratings completed including
		BPSD ¹⁰⁹ and quality of life ^{120,121}

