	Metrics (treatment adherence)	% of referred Latino ADRD dyads who attends at least 50% of
		Health Navigator visits
Acceptability	Dyad FU survey (6m)	5-item Likert scales on satisfaction with clinic and Health
		Navigator services

CONSIDERATIONS, POTENTIAL PITFALLS, AND LIMITATIONS

This study aims to assess the feasibility of Alianza Latina to inform the design and implementation of future, larger scale efficacy randomized controlled trials.²⁸ Because feasibility studies are not hypothesis testing studies, we have not planned to include a control group to evaluate efficacy. In this study we will administer pre- and post-intervention measures that will serve as efficacy outcomes in future randomized control trials (i.e. BPSD, quality of life). However, the main objective of those measurements in the current study is to evaluate assessment feasibility. If feasibility findings are favorable, we will conduct a fully-powered R01 RCT to assess efficacy and cost-effectiveness. If not favorable, we will use the qualitative information gathered in the study and new research to refine the intervention and test its new feasibility before conducting an efficacy trial. We have estimated that 10 clinics will recruit 100 ADRD participants in seven months. If recruitment is slow, we will identify Latino older adults in the community through our center's recurrent ADRD educational events, the Latino community network and the participant pool I developed during my Diversity Supplement and attempt to train their PCPs in the Alianza Latina services to speed up the process. A previous study trained and used abstracters to assess adherence to ADRD services recommendations at the clinics at all times. 122 This approach is not financially feasible for this project but will be considered for a future study. Because this intervention is multicomponent, it will not allow disentangling effects of specific components. We will attempt to deconstruct the intervention in future studies if results are favorable. Most information gathered is focused on the person with ADRD. Though we plan to gather more information from caregivers in the future, this is secondary. We acknowledge that the involvement of caregivers in the aid of people with MCI or mild ADRD might be much lower than that of moderate and late stages, which may affect feasibility and acceptability outcomes.

PROTECTION OF HUMAN SUBJECTS

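### The ±7.4% precision stated for 100/135 enrolling dyads matches the normal approximation; the exact binomial interval the plan specifies is -8.2/+7.2 points

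*Combined protocol and SAP*

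**What the plan says.** The point lies in the combined protocol and SAP, Aim 2, under *Data analysis and sample Size Justification*. The primary feasibility endpoints there are dichotomous and are to be reported as proportions. The interval method is named: "Results will include 95% confidence intervals based on an exact binomial distribution".

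The next sentence gives two planning assumptions: that 50 of 100 PCPs will take up the screenings, and that 100 of 135 referred dyads will enroll with the Health Navigator. The precision expected from these is stated as follows: "our confidence intervals will be within approximately ±11.0% and ±7.4%, respectively, of their estimated proportions".

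The section then says that the study is not powered for a hypothesis test and rests the sample size on "sufficiently accurate estimation of these important processes measures to inform the subsequent R01 application". It does not give the formula behind the two half-widths and does not name a variant of the exact interval.

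**The concern.** Two adjacent sentences appear to use different methods. An exact binomial interval around 74% is not symmetric: its lower arm is longer than its upper arm. A single ± figure therefore cannot describe it exactly, and ±7.4 is what the simple normal approximation gives. The companion ±11.0 for 50/100 is wider than either method gives.

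In a one-arm study that only estimates proportions, the stated precision is the sample size justification. These two half-widths are its only quantitative content, so a reader should be able to reproduce them from the stated method. For enrollment, the understated side is the lower one, which is the less favourable limit when planning recruitment for the later trial.

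The stakes are small. The decision rule under *Considerations, Potential Pitfalls, and Limitations* is qualitative: "If feasibility findings are favorable, we will conduct a fully-powered R01 RCT to assess efficacy and cost-effectiveness". No numeric limit is attached to it.

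**Working it through.** **Inputs**, all from *Data analysis and sample Size Justification*: 95% confidence; x/n = 100/135 = 0.7407 for dyads; x/n = 50/100 = 0.5000 for PCPs; stated half-widths 7.4 and 11.0 points. Two assumptions are added: the intervals are two-sided, and *exact* means Clopper-Pearson, the standard exact binomial interval.

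**Step 1. Reproduce the stated figures with the normal approximation**, 1.96 × √(p(1−p)/n).

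- 100/135: 1.96 × √(0.7407 × 0.2593 / 135) = 7.39 points, which rounds to the stated 7.4.
- 50/100: 1.96 × √(0.25 / 100) = 9.80 points, not 11.0.

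**Step 2. Apply the exact method.** The lower limit is the p at which P(X ≥ x) = 0.025, and the upper limit is the p at which P(X ≤ x) = 0.025. In beta quantiles these are the 2.5% point of Beta(x, n−x+1) and the 97.5% point of Beta(x+1, n−x).

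- 100/135: Beta(100, 36) gives 65.83% and Beta(101, 35) gives 81.23%. The arms are 74.07 − 65.83 = 8.24 below and 81.23 − 74.07 = 7.16 above, with mean half-width 7.70.
- 50/100: Beta(50, 51) gives 39.83% and Beta(51, 50) gives 60.17%. The arms are 10.17 on each side.

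**Step 3. Compare.**

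| Proportion | Stated | Normal approximation | Exact | Exact limits |
|---|---|---|---|---|
| 100/135 dyads | ±7.4 | ±7.39 | −8.24 / +7.16 | 65.8% to 81.2% |
| 50/100 PCPs | ±11.0 | ±9.80 | ±10.17 | 39.8% to 60.2% |

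The stated ±7.4 implies limits of 66.67% and 81.47% for dyads. The lower limit differs from the exact one by 66.67 − 65.83 = 0.84 points. For PCPs the stated figure is wider than the exact one by 11.0 − 10.17 = 0.83 points.

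**Step 4. Check whether another variant rescues ±7.4.** Results for 100/135:

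| Method | Below | Above | Mean half-width |
|---|---|---|---|
| Blaker | 8.03 | 6.86 | 7.44 |
| Minimum-likelihood exact | 8.11 | 6.73 | 7.42 |
| Mid-P | 7.88 | 6.86 | 7.37 |
| Wilson | 7.99 | 6.65 | 7.32 |

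In each of these the lower limit is more than 7.4 points below the estimate. For 50/100, the widest interval tried was the normal approximation with continuity correction, at ±10.30, so none reaches ±11.0.

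**The case against.** The strongest reply is that the sentence is hedged and nothing depends on it. It says *approximately*, and one symmetric figure for a mildly skewed interval is common planning shorthand. The mean exact half-width of 7.70 is only 0.3 points from 7.4, and the upper arm of 7.16 is inside it. The final analysis already uses exact intervals, and a lower limit of 65.8% instead of 66.7% would hardly change anyone's view of whether the estimate is accurate enough. This argument on consequence stands and sets the severity.

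A second reply concerns where ±7.4 came from. The plan gives no formula, so the normal approximation is inferred from the numerical match. Other calculations also come close. The mean half-widths of the Blaker and minimum-likelihood exact intervals round to 7.4, and the 2.5% and 97.5% quantiles of a Binomial(135, 100/135) count are 90 and 110, which is ±10/135 = ±7.41. The companion ±11.0 does not fit the normal approximation either. So the origin is not proven. The mismatch does not depend on it, though. The quantile range describes the spread of a count when the proportion is known and is not a confidence interval, and every exact variant tried has a lower arm longer than 7.4.

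A third reply is that the exact variant is unnamed. That is correct, so the specific −8.2/+7.2 depends on reading *exact* as Clopper-Pearson.

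The hedge does not fully cover the discrepancy. Both figures are given to one decimal, they are worded as outer bounds, and they miss in opposite directions: one is too tight on its lower side and the other too wide.

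**Conclusion.** The point holds and is minor. The stated precision for dyad enrollment is not what the plan's own method gives. The Clopper-Pearson interval for 100/135 is 65.8% to 81.2% (−8.2/+7.2 points), so the implied lower limit of 66.7% is about 0.8 points too favourable. The PCP figure is correct as a bound but about 0.8 points looser than the exact ±10.2.

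The exact dyad limits assume a two-sided Clopper-Pearson interval. That the lower arm exceeds 7.4 points also holds under the Blaker, minimum-likelihood exact and mid-P intervals. That ±7.4 was computed with the normal approximation is an inference from the match with 7.39. The effect is limited to the planning sentence.

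**What to change.** Name the interval and replace the two half-widths with exact limits, for example: *With an anticipated 50/100 PCPs and 100/135 referred dyads, the exact (Clopper-Pearson) 95% confidence intervals would be 39.8% to 60.2% (±10.2 points) and 65.8% to 81.2% (−8.2/+7.2 points).*

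If ±11.0 was meant to allow for something else, such as fewer PCPs than 100 answering the follow-up survey, state that assumption and the denominator used.

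The cost is one sentence. No participants are added, and the design, endpoints and analysis do not change. The enrollment lower limit will read about 0.8 points less favourably, and the PCP interval about 0.8 points tighter on each side.

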financial assistance applications for ADRD expenses. Further visits will continue the Chronic Care Plan, which will address the most pressing needs reported by the patient and caregiver. Table 2 includes potential patient and caregiver needs depending on ADRD stage. The Chronic Care Plan will use evidence- and consensus-based recommendations to address those needs, including Gitlin's non-pharmacologic management of behavioral symptoms protocol, the Reducing Disability in Alzheimer's Disease community program to promote functioning and caregiver support, the At the Crossroads kit for driving safety for individuals with ADRD the ADRD the resources. Community resources referred to by the Health Navigator will either provide bilingual services or include interpreters. If there is no other option, the Health Navigator will assist with interpretation.

Recruitment and retention. We will provide *Alianza Latina* Health Navigator-services to all Latinos diagnosed with ADRD by *Alianza Latina* PCPs, other clinicians, or the research team. Outreach will include multiple inperson (i.e., clinic referrals and health events) and remote methods (i.e., calls from research registries, online advertising and flyers). We will enroll 100 Latino ADRD patients. The Health Navigator will contact participants to schedule a consent and BL appointment during their first visit. Participants who sign the informed consent will be enrolled. To reduce attrition, we will collect contact information from an alternate contact person and staff will keep flexible hours and allow home visits. Participants will receive \$40 pre-paid cards for completing assessments at BL and FU. All materials developed by the research team will be bilingual and follow World Health Organization translation and back translation guidelines.¹¹⁶

Eligibility Criteria: 1) identify as Latino, 2) community dwelling, 3) diagnosed with MCI or ADRD by *Alianza Latina* PCPs, other clinicians, or the research team, 5) have a caregiver 18 years old or older and 6) access to a privately-owned cell phone with a flat rate fee for text messages.

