Recruitment Estimates. Based on the primary care population of our clinics, each serves an average of 12 Latino individuals/day. We expect 12% to be 65 and older based on the Census. In 261 working days, they will serve 376 Latinos 65+. Because ADRD prevalence among Mexican-Americans is 10%, we expect 38 Latinos 65+ with ADRD per year per clinic. In a conservative scenario, 66% of those with ADRD have never been diagnosed (28 per clinic). Research shows that 74% of ADRD patients are willing to participate in Health Navigator services, which reduces the number to 18 per clinic. Because there will be approximately 10 clinics, the time needed to recruit 100 participants will be approximately seven months.

Assessment Procedures and Measures. Assessments will include metrics and survey information to Latino ADRD patients and their caregivers based on standard criteria for outcomes in feasibility studies (Table 3). BL surveys will include sociodemographic data: age, gender, marital status, educational level, insurance type, household income, Latino origin and caregiver relationship 118 and acculturation: English preference, place of birth and years in the USA. 119 Metrics will assess enrollment in Health Navigator services, six-month retention,

completion of BL and FU assessments (i.e. BPSD and quality of life scales) and adherence to Health Navigator visits. FU surveys will assess satisfaction with the *Alianza Latina* Health Navigator services.

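### Table 3 computes six-month retention and visit adherence over referred rather than enrolled dyads, which caps both at 74.1% under the plan's own enrolment forecast

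*Combined protocol and SAP*

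**What the plan says.** Table 3 (Feasibility and acceptability outcomes in Aim 2) uses one denominator for three ADRD care metrics:

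- Recruitment: the percentage "of referred Latino ADRD dyads who enroll in Health Navigator" services.
- Retention: the percentage "of referred Latino ADRD dyads followed up at 6m".
- Treatment adherence: the percentage "of referred Latino ADRD dyads who attends at least 50% of" Health Navigator visits.

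The Data analysis and sample Size Justification section anticipates "100/135 newly referred Latino ADRD dyads who enroll in Health Navigator services". It says that the primary feasibility endpoints are dichotomous, "so the proportions will be estimated as the main statistical results", each with an exact binomial 95% confidence interval.

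Under Aim 2.b, Recruitment and retention states: "Participants who sign the informed consent will be enrolled". The measures to limit attrition come directly after that sentence. The same aim places the first Health Navigator visit at the baseline assessment. Assessment Procedures and Measures treats the metrics as distinct: "Metrics will assess enrollment in Health Navigator services, six-month retention", followed by assessment completion and visit adherence. No section redefines retention or adherence over enrolled dyads.

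**The concern.** Retention and treatment adherence normally describe what happens after a participant joins. Here both denominators include dyads who never joined. A referred dyad that does not consent stays in the denominator and cannot enter either numerator, so non-enrolment is counted once under recruitment and again under the other two rows.

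Low uptake and dropout after enrolment are different problems and call for different changes to the intervention. A retention figure that mixes them will read as worse retention than occurred. It will also move with the outreach mix: Aim 2.b accepts dyads from flyers and online advertising as well as from clinicians, and a lower consent rate from any source would depress reported retention even if enrolled dyads behaved identically.

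The results feed a decision. Under Considerations, Potential Pitfalls, and Limitations: "If feasibility findings are favorable, we will conduct a fully-powered R01 RCT"; otherwise the intervention is refined and retested. The plan gives no numerical definition of favorable, so the judgement rests on how the reported percentages are read.

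**Working it through.** **Inputs from the plan.** 100 enrolled of 135 referred, and exact binomial 95% intervals (Data analysis and sample Size Justification); denominators from Table 3; enrolment only on signed consent (Recruitment and retention).

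**Inputs assumed.** The plan forecasts neither retention nor adherence. I take x = 70, 80 or 90 of 100 enrolled dyads meeting the criterion. The same arithmetic applies to either metric.

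**Plan's own figure.** For 100/135 the plan states a precision of about ±7.4%. The normal approximation gives 1.96 × √(0.7407 × 0.2593 / 135) = 7.39 points, which reproduces it. (The exact interval that the plan names is 65.8% to 81.2%, that is −8.2/+7.2 points.) So 135 is the number referred, and 135 − 100 = 35 are forecast not to enrol.

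**Relation between the two rates.** Referred-based rate = x/135 = (x/100) × (100/135) = enrolled-based rate × 0.741. The maximum, at x = 100, is 74.1%.

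**Results** (exact Clopper-Pearson 95% intervals):

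| x retained | Table 3 rate, x/135 | Enrolled-based rate, x/100 | Gap (points) | Shortfall due to non-enrolment, 35/(135 − x) |
|---|---|---|---|---|
| 70 | 51.9% (43.1 to 60.5) | 70.0% (60.0 to 78.8) | 18.1 | 35/65 = 53.8% |
| 80 | 59.3% (50.5 to 67.6) | 80.0% (70.8 to 87.3) | 20.7 | 35/55 = 63.6% |
| 90 | 66.7% (58.0 to 74.5) | 90.0% (82.4 to 95.1) | 23.3 | 35/45 = 77.8% |

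In every row the Table 3 estimate lies below the whole enrolled-based interval. Non-enrolment is exactly half of the shortfall at 65 retained (35/70) and less than half below that: 46.7% at 60 (35/75) and 41.2% at 50 (35/85).

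**Sensitivity to the forecast.** The ceiling is whatever enrolment proportion is observed. With 100 enrolled from 120 referred it is 83.3%; from 150 it is 66.7%.

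**Recoverability.** Dividing by the recruitment proportion restores the point estimate: 59.3/74.1 = 80%. It does not restore the interval. Dividing the limits in the same way gives about 68% (50.5/74.1) to 91% (67.6/74.1), against 70.8% to 87.3% computed directly from 80/100.

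**Effect on the R01.** If a sample size is divided by the expected retention r, using 0.741r instead inflates it by 1/0.741 = 135/100 = 1.35. This happens only if the Table 3 figure is used directly as a retention rate. If it is first divided by the recruitment proportion, there is no inflation.

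**The case against.** The strongest reply is that the documents use the word referred in two senses. Aim 2.b applies it to the 100 dyads who receive the service, so the retention and adherence rows might mean enrolled dyads. The loose sense is impossible only in the recruitment row, where it would give 100/100 and contradict the 100/135 forecast. It can be added that a non-enrolled dyad has no planned visits, so its adherence is undefined rather than failed, and that an analyst could sensibly restrict both rows to enrolled dyads.

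That shows that the intention may have been sound, but it does not change what the table says. The identical phrase appears in three rows of one table, and nothing signals a change of meaning between them. Nor is a dyad's adherence left undefined: the metric is a proportion of referred dyads, so a non-enrolled dyad is in the denominator and cannot be in the numerator.

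Three other points have force:

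- For a health-systems intervention, the share of referred dyads reached at six months is a legitimate pathway measure. No section declares it as such, however, and the rows are labelled retention and treatment adherence.
- The enrolled-based rate is recoverable from the same counts, and the team intends to review all results together before sizing the next trial.
- No threshold, sample size or stated precision in this study depends on these two rows.

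These points limit the consequence. They do not remove the mislabelling.

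**Conclusion.** The concern holds. Followed as written, Table 3 yields retention and adherence rates equal to the enrolled-based rates times the enrolment proportion: a factor of 0.741 and a ceiling of 74.1% under the plan's forecast. For assumed enrolled-based rates of 70% to 90%, the understatement is 18 to 23 points, and non-enrolment accounts for more than half of the reported shortfall.

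This rests on the 100/135 forecast and on non-enrolled dyads contributing no visits or six-month data, which the consent and visit text supports. The retention levels are illustrations, not forecasts. No decision rule is broken and no data are lost. The fault is that two reported proportions and their intervals would describe a different quantity from the one named, in a study whose purpose is to estimate such quantities for the next trial. It should be corrected before analysis.

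**What to change.** In Table 3, under ADRD care, replace the word referred with enrolled (signed consent) in the retention row and in the treatment adherence row. Leave the recruitment row as it is. If whole-pathway yield is wanted, add a separate line under that name for the referred-based figure. Report the numerator and denominator counts with each percentage.

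The cost is table wording, plus one line if pathway yield is kept; no new data or participants are needed. The denominator falls from about 135 to 100, with little effect on precision. The full width of the exact 95% interval changes from 17.4 to 18.7 points at 70% assumed retention, from 17.2 to 16.5 at 80%, and from 16.5 to 12.7 at 90%.

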Aim 2.b. Providing Latino ADRD patients with enhanced ADRD chronic care through Health Navigators. The Health Navigator will be the single-point-of-contact between the patient and the PCP. The Health Navigator will be a Bachelor's degree-level individual with experience working with the Latino community in health-related projects and will be trained and supervised closely by [name] Worker team. The training will include the ACT on Alzheimer's online course for care managers, a Dementia Intensive one-day course from the KU ADC and progressive shadowing to achieve independence supervised weekly by [name] team. The KU ADC recently had a highly successful Dementia Intensive training for Social Workers drawing nearly 100 social work students from 7 colleges in the region and significantly increasing their levels of objectively assessed ADRD knowledge. The first Health Navigator visit will be in-person and will coincide with the BL assessment. The Health Navigator will perform a Clinical Intake Assessment using validated instruments when possible including the Brief Neuropsychiatry Inventory Questionnaire, Geriatric Depression Scale or the Functional Assessment

Table 2. ADRD needs addressed by the Chronic Care Plan

MCI	Prevent behaviors, slow cognitive decline,		
Patient	engagement, legal planning		
Caregiver	Caregiver support, legal planning & training		
Early & moderate ADRD Patient	Safety, security, engagement, functioning, behavioral management, pain, sleep co- morbidities, legal planning		
Caregiver	Caregiver support and training, respite, stress reduction, legal planning		
Severe ADRD Patient	Stress, anxiety, agitation, pain		
Caregiver	Caregiver support, end of life care, counseling, role resumption		

Questionnaire. 109 The initial Clinical Intake Assessment will result in a written "Chronic Care Plan" that will be provided to the dyad and encouraged to be shared with their PCP. The Health Navigator will enroll the co-participant in *CuidaTEXT* a culturally tailored text message program to educate Latino caregivers on ADRD care. 110 Educating families is important among Latinos as decision-making is more likely to be shared by multiple relatives. 111 Given that Latinos are among the groups with the lowest income in the USA, 112 Health Navigators will inform participants about available

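### Dyad assessment completion is a percentage of ratings, and an exact binomial interval on the rating count would ignore correlation within dyads and is likely to be too narrow

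*Combined protocol and SAP*

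**What the plan says.** Table 3, under ADRD care feasibility (assessment process), reports the percentage "of planned BL and FU survey ratings completed including" BPSD and quality of life. The other percentage rows in the table count PCPs or dyads. The matching PCP row is the percentage "of PCPs who complete BL and FU surveys about ADRD" knowledge, attitudes and skills, and the dyad retention row is the percentage "of referred Latino ADRD dyads followed up at 6m".

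The section on data analysis and sample size justification states: "The primary quantitative feasibility/process endpoints are dichotomous measures, so the proportions will be estimated as the main statistical results". It then says: "Results will include 95% confidence intervals based on an exact binomial distribution". It names no other interval method, whether clustered, resampled or based on dyads. Its two worked precision figures are for other rows: 50/100 PCPs and 100/135 dyads. It gives no denominator, expected completion or precision for the ratings row.

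The Aim 2.b section on assessment procedures and measures describes the same metric as "completion of BL and FU assessments (i.e. BPSD and quality of life scales) and adherence to Health Navigator visits". The number of scales per visit is not stated.

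**The concern.** An exact binomial interval assumes independent trials. Ratings from one dyad are not independent: at least two constructs are rated at each of two visits, and a dyad that is not seen at six months misses all its follow-up ratings at once. If the number of ratings is used as the sample size, the interval claims more information than 100 dyads provide. Adding questionnaires would then narrow it without adding any dyad.

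The row matters because the limitations section says that BPSD and quality of life are measured in this study mainly to learn whether they can be assessed, and that they are intended as efficacy outcomes of the later randomised trial. The study also justifies its size by accuracy of estimation rather than by power, so the width of an interval is part of what it delivers.

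**Working it through.** **The plan's own figures.** There is none for this row. The two that are given use people or dyads as the unit. For 50/100 the exact half-width is ±10.2 points against the stated ±11.0. For 100/135 it is ±7.7 on average against the stated ±7.4, which is the normal-approximation value. Those differences are a separate matter and do not come from the unit of analysis.

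**Inputs from the documents**
- Dyads: 100 ("We will enroll 100 Latino ADRD patients").
- Visits with ratings: two, baseline and follow-up.
- Ratings per visit, K: at least 2 (BPSD and quality of life). The count is not given.

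**Assumptions**
- Baseline is complete. This is plausible among enrolled dyads: "The first Health Navigator visit will be in-person and will coincide with the BL assessment".
- Follow-up completion q = 0.70, with 0.60 to 0.90 as the range.
- Within-dyad correlation of follow-up ratings r: 1 (all-or-none loss), 0.5 or 0.2.
- K = 2, 3 or 5.

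**Formulas.** The row pools both visits, so there are 200K planned ratings and the expected completion is p = (1 + q)/2 = 0.85.

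- Variance if ratings are independent: p(1 − p)/(200K) = (1 + q)(1 − q)/(800K).
- Actual variance: q(1 − q)[1 + (K − 1)r]/(400K).
- Ratio of actual to assumed variance: 2q[1 + (K − 1)r]/(1 + q).
- The ratio exceeds 1 when r > [(1 + q)/(2q) − 1]/(K − 1).

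**Numbers for K = 2, q = 0.70**
- Exact binomial on 340/400: 81.1% to 88.4%, or ±3.6 points.
- Correct half-width at r = 1: 1.96 × √(0.7 × 0.3/400) = ±4.5.
- At r = 0.5: 1.96 × √(0.21 × 1.5/800) = ±3.9.
- At r = 0.2: 1.96 × √(0.21 × 1.2/800) = ±3.5.
- Break-even r: (1.7/1.4 − 1)/1 = 0.21. For K = 3 it is 0.11.

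**Simulated coverage of the nominal 95% interval** (pooled row, 100 dyads, q = 0.70, 40,000 simulated studies per cell; r = 0.5 by beta-binomial)

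| Ratings per visit | r = 1 | r = 0.5 |
|---|---|---|
| 2 | about 90% | about 93% |
| 3 | about 77% | about 88% |
| 5 | about 67% | about 80% |

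At r = 0.2 with two ratings per visit, coverage is 96%, so there is no shortfall.

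**Sensitivity to retention.** With q from 0.60 to 0.90, K = 2 and all-or-none loss, coverage runs from 86% to 90%. With K = 4 it runs from 72% to 76%. The result depends more on the number of ratings and their correlation than on the assumed retention.

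**The case against.** The plan never says that the interval for this row takes the number of ratings as its sample size. It ties the exact binomial to dichotomous primary endpoints and illustrates it only with PCPs and dyads. Reporting completion for each scale at each visit would fit the wording in the assessment section and would make the exact interval valid. This stands in part: the calculation is an inference from the row's definition, not a stated step. But a percentage of ratings has ratings as its natural denominator, and the plan offers no other method, so a literal reading leads to the problem.

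Three stronger readings are tempting, and the documents do not support them.

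- *A large error.* A reader might look at follow-up ratings alone: 140/200 gives an exact ±6.6 against ±9.4 for 70/100 dyads. The row pools baseline and follow-up, however, and with two ratings per visit the pooled gap is about 0.9 point (4.5 − 3.6).
- *An interval that must be too narrow.* Completed baseline ratings add no variation, so some follow-up correlation is needed before the interval becomes too narrow. Loss of whole visits makes that likely, not certain.
- *A wrong figure or decision.* No stated precision relates to this row, the outcomes are descriptive, and no test or progression threshold uses the interval. The percentage itself is unaffected.

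It is also fair to say that six-month loss already appears at dyad level in the retention row. That limits the consequence but does not make the interval for this row valid.

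**Conclusion.** The point holds in a limited form. Table 3 counts ratings, the only stated interval method assumes independence, and nothing in the plan accounts for several ratings from one dyad. Applied to the rating count, the interval is likely to be too narrow. Under all-or-none loss with 70% follow-up and complete baseline, the documented minimum of two ratings per visit gives ±3.6 points instead of about ±4.5. The shortfall grows with the number of scales and shrinks with weaker correlation, and both quantities are absent from the plan. This is worth correcting because precision of estimation is the study's stated purpose and the correction is cheap. It does not invalidate any figure in the plan.

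**What to change.** State the denominator for this row and choose one of two routes.

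1. Keep the percentage of planned ratings and take its 95% interval from a bootstrap that resamples whole dyads.
2. Report completion separately for each scale and visit, with dyads as the denominator. Each dyad then contributes one observation to each proportion, and the exact binomial interval is valid under the plan's existing rule.

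The percentage of dyads with every planned rating complete may be added as a supplement. It should not replace the row, because it treats a dyad that missed one scale like a dyad that was lost, and so discards the information on partial completion.

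The cost is one extra analysis sentence and a somewhat wider interval under the first route, or at least four proportions in place of one under the second. No extra data, visits or participants are needed.
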